    call symput("seed", strip(put(seed,12.)));
    keep boot subj;
run;

* match the subject number to retrieve other subject-specific data;
proc sql noprint;
    create table bootsamp as
    select b.boot, a.subj, a.treated, a.followup, a.time, a.status a.complete a.episode
    from raw as a, bootid as b
    where a.subj=b.subj
    order by boot, subj;
quit;

* obtain posterior draws of model parameters from bootstrap samples;
proc phreg data=bootsamp;
    by boot;
    class episode region treated(ref='1');
    model time*status(0)=episode region treated;
    bayes nmc=%eval(&nimps*&thin) piecewise=hazard seed=314;
    ods output Partition=partition PosteriorSample=postsamp;
run;
ods output close;

* Boot samp data for both treatments
data bootsamp1;
set bootsamp;
if treated in (1,2); * Placebo Vs 1.5mg;
run;

data bootsamp2;
set bootsamp;
if treated in (1,3); * Placebo Vs 3.0;
if treated=3 then treated=2;
run;

/*Delta-Adjusted Method*/
%macro delta(postsamp=, bootsamp=, trt=, dataout=);

data postsam2;
    set &postsamp.;
    temp = (Iteration - 2000 - 1)/&thin + 1;
    _imputa_ = floor(temp);
    if _imputa_ = temp;
    rename &trt.=beta;
    keep boot _imputa_ lambda1-lambda&ninterval &trt.;
run;

```

```

*merge with raw data;
proc sql noprint;
    create table raw2 as
        select a.* , b.subj, b.treated, b.followup, b.time, b.status, b.complete, b.episode
        from postsam2 as a, &bootsamp. as b
        where a.boot=b.boot
        order by boot, _imputa_, subj;
quit;

* obtain maximum follow-up;
proc univariate data=&bootsamp. noprint;
    by boot;
    var time;
    output out=maxtime max=maxtime; * maximum survival time;
run;

* organize partition information;
proc transpose data=partitit out=partitit(drop=_name_ _label_)
    prefix=a;
    by boot;
    var UpperTime;
run;

data partitit;
    merge partitit maxtime;
    by boot;
    a&ninterval = maxtime+1; * a large number to represent infinity;
    drop maxtime;
run;

data raw2;
    merge raw2 partitit;
    by boot;
run;

* impute censored event times for early dropouts;
data raw4;
    set raw2 end=eof;
    if _n_=1 then seed=789;
    retain seed;

    array a{&ninterval};
    array lambda{&ninterval};

    call ranuni(seed, u);
    do delta=0 to 2 by 0.147;
    nlogu = -log(u)/exp(treated*(beta+delta)); * MNAR;

    * no imputation needed for subjects with events or for completers;
    if status=1 or (status=0 and time=followup) then do;
        time3 = time;
        status3 = status;

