        miphest2(keep=boot delta estimate stderr lclmean uclmean);

```

```

by boot delta;
plogrank = probt;
hazardra = exp(estimate);
hrlowerc = exp(lclmean);
hrupperc = exp(uclmean);
*drop probt estimate lclmean uclmean;
run;

proc sort data=miout2a out=miout2b;
  by delta boot;
  where boot>0;
run;

proc univariate data=miout2b nopolish;
  by delta;
  var estimate;
  output out=miout2c std=StdErrbo;
run;

data miout2;
  merge miout2a(where=(boot=0)) miout2c;
  by delta;
  bhrlower = exp(estimate - 1.96*stderrbo);
  bhrupper = exp(estimate + 1.96*stderrbo);
  label stderrbo=" ";
run;

data &dataout.;
  format Analysis $20.;
  set miout2(in=b);
  analysis="Sensitivity";
  drop boot probt lclmean uclmean;
  format estimate stderr stderrbo bhrlower bhrupper 8.3;
run;

%mend;

%delta(postsamp=postsamp, bootsamp=bootsamp1, trt=treated2, dataout=sensi3);
%delta(postsamp=postsamp, bootsamp=bootsamp2, trt=treated3, dataout=sensi4);

* /*placebo-based pattern mixture model*/
%macro pattern(postsamp=, bootsamp=, trt=, dataout=);*;

data postsam2;
  set &postsamp.;
  *set postsamp;
  temp = (iteration - 2000 - 1)/&thin + 1;
  _imputa_ = floor(temp);
  if _imputa_ = temp;
  rename &trt.=beta;
  *rename treated2=beta;
  keep boot _imputa_ lambda1-lambda&ninterval &trt.;
run;

* merge with raw data;
proc sql nopolish;
  create table raw2 as
  select a.*, b.subj, b.treated, b.followup, b.time, b.status, b.episode
  from postsam2 as a, &bootsamp. as b
  where a.boot=b.boot
  order by boot, _imputa_, subj;
quit;

* obtain maximum follow-up;
proc univariate data=&bootsamp. nopolish;
  by boot;
  var time;
  output out=maxtime max=maxtime; * maximum survival time;
run;

* organize partition information;
proc transpose data=partitio out=partitit(drop=_name_ _label_) prefix=a;
  by boot;
  var uppertime;
run;

```

```

data partitit;
  merge partitit maxtime;
  by boot;
  a&ninterval = maxtime+1;  * a large number to represent infinity;
  drop maxtime;
run;

data raw2;
  merge raw2 partitit;
  by boot;
run;

* impute censored event times for early dropouts;
data raw3;
  set raw2 end=eof;
  if _n_=1 then seed=789;
  retain seed;

  array a{&ninterval};
  array lambda{&ninterval};

  call ranuni(seed, u);
  do phi=0 to 1 by 0.2;
  nlogu = -log(u)/exp(treated*(1-phi)*beta ); * MNAR;

  * no imputation needed for subjects with events or for completers;
  if status=1 or (status=0 and time=followup) then do;
    time3 = time;
    status3 = status;
  end;

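### The imputation lines in SAP Appendix II use a 1/2 treatment code where a 0/1 code is needed, so both sensitivity analyses impute dropouts in both arms at the wrong hazard

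*SAP*

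**What the plan says.** SAP Section 10.1 describes two sensitivity analyses for informative censoring. In the first, delta raises the post-dropout hazard in the experimental arm and is increased until significance is lost; clinicians then judge whether the tipping-point delta is plausible. In the second, placebo dropouts are assumed to fare like placebo patients who stayed, and cariprazine dropouts have hazard h0(t)·exp((1−phi)·beta). There phi = 0 is noninformative censoring and phi = 1 is the full placebo-based assumption.

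Appendix II turns this into code:

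- The posterior model has the class statement "class episode region treated(ref='1", so level 1 is the reference.
- The 1.5 mg comparison is selected by "if treated in (1,2); * Placebo Vs 1.5mg". The 3.0 mg comparison keeps codes 1 and 3, and then "if treated=3 then treated=2" applies.
- The delta macro imputes with "nlogu = -log(u)/exp(treated*(beta+delta)); * MNAR" over the grid "do delta=0 to 2 by 0.147".
- The pattern-mixture macro imputes with "nlogu = -log(u)/exp(treated*(1-phi)*beta ); * MNAR".
- Both macros retain posterior draws with "keep boot _imputa_ lambda1-lambda&ninterval &trt", that is, the interval hazards and the one treatment coefficient.

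**The concern.** The formula in each imputation line is right for a treatment variable coded 0 for placebo and 1 for cariprazine. The variable supplied to it is coded 1 and 2. Dropouts in both arms therefore carry one factor too many: exp(beta+delta) in the delta macro and exp((1−phi)·beta) in the pattern-mixture macro.

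Three features of Section 10.1 are lost. Delta is no longer confined to cariprazine. Placebo dropouts no longer follow continuing placebo patients. The starting points delta = 0 and phi = 0 no longer represent noninformative censoring.

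The delta analysis is the more exposed of the two. Section 10.1 gives no formula for delta, so the Appendix II line is its only numerical definition. Clinicians would be asked to judge a number that is not the hazard increase actually applied.

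**Working it through.** **1. Coding.** The filters and the recode leave placebo = 1 and cariprazine = 2 in both two-arm data sets. Because level 1 is the reference, the interval hazards (lambda) are placebo hazards and beta is the log hazard ratio of cariprazine to placebo. The same lambda is used for every dropout, so arm enters only through the imputation line. Appendix I mentions treatment codes 0 and 1, but that does not rescue the line: the Appendix II filters would delete a placebo arm coded 0.

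**2. Algebra.** Let x = beta + delta, or x = (1−phi)·beta.

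- Intended multiplier on lambda: placebo 1, cariprazine exp(x).
- Coded multiplier: placebo exp(x), cariprazine exp(2x).

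The ratio between arms is still exp(x); the level is wrong in both arms by the factor exp(x). The error vanishes only when x = 0, that is, at phi = 1 or delta = −beta.

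**3. Size at the planned hazard ratio.** SAP Section 14.0 assumes HR 0.42, so beta = ln 0.42 = −0.868. The grid ends at 13 × 0.147 = 1.911.

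| Setting | Intended (placebo / cariprazine) | As coded |
|---|---|---|
| delta 0 | 1 / 0.42 | 0.42 / 0.176 |
| delta 0.441 | 1 / 0.653 | 0.653 / 0.426 |
| delta 0.868 (= −beta; not a grid point) | 1 / 1 | 1 / 1 |
| delta 1.47 | 1 / 1.827 | 1.827 / 3.337 |
| delta 1.911 | 1 / 2.839 | 2.839 / 8.061 |
| phi 0 | 1 / 0.42 | 0.42 / 0.176 |
| phi 0.4 | 1 / 0.594 | 0.594 / 0.353 |
| phi 1 | 1 / 1 | 1 / 1 |

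Relative to patients who continue in the same arm, the applied increase is exp(2x)/exp(beta) = exp(beta + 2·delta) for cariprazine and exp(beta + delta) for placebo:

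- delta 1.617: nominal exp(1.617) = 5.0; applied 10.7 for cariprazine and 2.1 for placebo.
- delta 1.911: nominal 6.8; applied 19.2 and 2.8.

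**4. Check of the planning scenario.** Inputs from Section 14.0: 126 per arm, 35% placebo relapse at Week 39, HR 0.42 for both doses, 26% early discontinuation. With exponential times and 39 weeks as the time unit, the relapse rates are −ln 0.65 = 0.431 for placebo and 0.42 × 0.431 = 0.181 for cariprazine, and the dropout rate is −ln 0.74 = 0.301. Expected relapses per arm are 126 × r/(r + 0.301) × (1 − exp(−(r + 0.301))), which gives 38.5 for placebo and 18.1 for each dose. The total is 74.7, against about 75 in the plan.

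**5. Effect on the tipping point.** Trials were simulated under that scenario with a three-arm piecewise-exponential posterior (8 intervals), log-rank results combined by Rubin's rule, and strata omitted. The main run had 2,000 trials and 50 imputations; 1,776 trials were significant before imputation.

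- Paired by trial, the coded tipping point differs in 53%: earlier in 51%, later in 2.5%. It is earlier by one grid step in 28%, by two in 20% and by three or more in 3%.
- With 200 imputations (537 significant trials) 52% differ. If 26% is read as observed dropouts (882 significant trials), 55% differ.
- In 8% to 11% the code tips inside the grid although the correct analysis stays significant to 1.911. In the main run, 33% of trials never tip as coded and 43% never tip when correct.
- Imputed placebo relapses run from 2.5 (delta 0) to 11.9 (delta 1.911) as coded; correctly they are 5.7 at every delta. Imputed cariprazine relapses are 1.2 instead of 2.7 at delta 0, and 20.6 instead of 12.9 at delta 1.911.
- Pattern mixture: imputed placebo relapses rise from 2.5 to 5.7 over the phi grid instead of staying at 5.7. Significance differs at one or more of the six phi points in 3% to 4% of trials, never at phi = 1.

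A separate large-sample calculation with known parameters gives the same direction. Z is −2.34 intended and −2.02 coded at delta 1.47, and −1.80 and −1.42 at delta 1.911.

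**The case against.** Section 10.1 calls these sample programs, and its prose is correct. The listing cannot run as printed: SQL commas are missing, a comment is not closed, a macro variable is defined under one name and used under another, and region is modelled but not carried forward. Production code must be rewritten and may not keep these lines. The simulated figures assume every other fault is repaired, so they isolate this formula and are not the listing's literal output. All of that stands.

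The consequence is also limited. No numeric delta decides pass or fail. The error mostly makes the result look less robust, and often by a single grid step. The between-arm ratio is preserved, the pattern-mixture conclusion barely moves, and the primary log-rank test, Cox model and sequential testing are unaffected. These points limit the weight of the finding.

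They do not remove it. The prose fixes the arm and the direction of delta but not its scale, so a programmer would take the scale from this line. Appendix IV records that Amendment 3 changed the appendix code (to add region), and these lines are still there.

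**Conclusion.** The lines are wrong as written and should be fixed. The coding error and the multipliers follow from the SAP alone and do not depend on simulation.

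Under the planning assumptions (exponential times, HR 0.42, 35% placebo relapse, 26% dropout, other code faults repaired), the reported tipping point would be too early in about half of significant trials, understating robustness in those, and too late in 2.5%. The paired difference is the firm result. The medians (1.62 coded, 1.76 correct) are less stable, since quarter-batches of the main run give 1.76 to 1.91 for the correct analysis. The effect on the pattern-mixture analysis is small.

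A secondary fault sits in the same step. The episode and region coefficients are in the fitted model but are not retained, so every dropout is imputed at the reference-level hazard. The documents do not allow the size of that effect to be determined.

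**What to change.** 1. Define `act=(treated=2)` and use `exp(act*(beta+delta))` and `exp(act*(1-phi)*beta)`. Leave `treated` as 1/2, because the later log-rank steps select on `treated=1`.
2. Keep the posterior episode and region coefficients, add them to the imputation linear predictor, and carry region through raw1, bootsamp, raw2 and the raw3/raw4 keep lists.
3. Tabulate imputed relapses by arm. The random draw "call ranuni(seed, u" is made once per dropout and imputation, before the loop over delta or phi, so placebo counts must be identical at every grid value. At delta = 0 and phi = 0, both arms must match the counts expected from the fitted hazards, within imputation error. In the main run, the placebo count at delta = 0 divided by its expected value was 0.10 to 0.72 as coded and 0.83 to 1.20 when correct, with no overlap in 1,776 trials.
4. Do not use agreement of the delta = 0 log-rank statistic as the check. Mean |Z| was 3.33 unimputed, 3.29 coded and 3.33 correct, which is too close to reveal the error.
5. In the same edit, reconcile `status=(cnsr=0)` in Appendix II with Appendix I, where 0 means censored. If Appendix I governs, the printed line swaps events and censoring.

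The cost is a few lines of SAP code, carrying region through the listing, and one count table. No new data are needed.

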APPENDIX III. REPORTING SELECTED LABORATORY PARAMETERS IN CONVENTIONAL UNITS

All clinical laboratory parameters will be reported in the International System (SI) units as standard practice. In addition, descriptive statistics for values and changes from baseline in conventional units at all assessed visits will be reported for selected laboratory parameters as listed in [Table 20-1](#) below.

Table 20-1. List of Selected Parameters to be Reported in Conventional Units

Number	Laboratory Parameter	Conventional Unit
1	Alanine Aminotransferase (SGPT)	U/L
2	Albumin	G/dL
3	Alkaline Phosphatase	U/L
4	Aspartate Aminotransferase (SGOT)	U/L
5	Bilirubin, Direct (Conjugated)	mg/dL
6	Bilirubin, Indirect (Unconjugated)	mg/dL
7	Bilirubin, Total	mg/dL
8	Blood Urea Nitrogen	mg/dL
9	Calcium	mg/dL
10	Cholesterol, HDL	mg/dL
11	Cholesterol, LDL	mg/dL
12	Cholesterol, LDL direct and calculated (combined) (This lab parameter could be the same as #11)	mg/dL
13	Cholesterol, Total	mg/dL
14	Creatine Kinase	U/L
15	Creatinine	mg/dL
16	Glucose	mg/dL
17	Insulin	uIU/mL
18	Triglycerides	mg/dL
19	Uric Acid	mg/dL
20	Hemoglobin	G/dL

Patients narratives will also include the values in conventional units for the selected lab parameters. That might be accomplished by presenting the values in conventional units within the parentheses next to the values in SI units.

APPENDIX IV. SAP AMENDMENT SUMMARY

Title: A Double-blind, Placebo-Controlled, Randomized Withdrawal, Multicenter Clinical Trial Evaluating the Efficacy, Safety, and Tolerability of Cariprazine in a Dose-reduction Paradigm in the Prevention of Relapse in Bipolar I Disorder Patients Whose Current Episode is Manic or Depressive, With or Without Mixed Features

Study RGH-MD-25 SAP Amendment #1 (28 February 2019)

Study RGH-MD-25 SAP Amendment #2 (13 June 2022)

Study RGH-MD-25 SAP Amendment #3 (23 November 2022)

Amendment Summary

This summary includes changes made to SAP RGH-MD-25 (11 October 2017).

Minor editorial and document formatting revisions have not been summarized. The following is a summary of the major changes that were made to each section of the SAP, and a brief rational for these changes.

SAP Amendment	Section	Major Revision	Rationale
#1	Global	Depressive with or without mixed feature as one more current Episode was added.	To align with Protocol Amendment #3. Depressive episodes have been included as potential index episodes following proven efficacy in bipolar I depression (RGH-MD-56 and RGH-MD-54).
#1	Global	Doses (Open-Label Period – Changed from 4.5 mg to 3.0 mg; DB Period: 2 Cariprazine Dose arms are now: 3.0 mg and 1.5 mg) were changed.	To align with Protocol Amendment #3. Depressive episodes have been included as potential index episodes, so OL dose was adjusted to reflect efficacy dose range in both bipolar I manic and bipolar I depressed patients.
#1	Section 4.0, Table 4-2	Visit schedule was changed. Day 4 and Day 10 study visits were deleted and a Day 22 visit was added. Study Visits have been renumbered throughout entire amendment 2. Study days have been renumbered to allow 1 full week of dosing before Visit 3 (Day 8).	Day 22 Visit was added to improve the potential to capture remission/stability criteria during the first weeks of OL treatment.

SAP Amendment	Section	Major Revision	Rationale
#1	Table 4-2	Symbol Digit Coding (SDC) – additional efficacy assessment was deleted.	Operational concerns, and clinical decision to remove cognitive battery
#1	Table 4-2	Visit windows of +3 days for Visit 2/Baseline and ± 3 days for Visits 3 through 33 to the table header were added.	For clarity
#1	Table 4-2	“Blood Alcohol Level” was changed to “Blood Alcohol Concentration by Breathalyzer”.	To expedite turnaround time for blood alcohol concentration results
#1	Table 4-2	Serum pregnancy tests at Visits 7, 18, 24, and 33 were added.	For clarity and for consistency with approved labeling
#1	Table 4-2	Text to clarify the timing of visits was added.	For clarity
#1	Section 4.0, Section 10.1	MADRS total score was changed from MADRS total score ≥ 17 to ≥ 20.	To align MADRS discontinuation score with moderate depression. MADRS ≥ 17 is considered mild depression and may not be suggestive of a true depressive episode
#1	Section 6.4	OL SFU population was added.	For analysis clarity
#1	Section 6.6	One paragraph “patients will be included in the treatment group corresponding to the DB IP they actually received regardless of the treatment they were randomized to” was added.	For clarity
#1	Section 6.7	One paragraph “patients will be included in the randomized treatment group for the DB ITT population” was added.	For clarity
#1	Section 8.0	The rescue medication categories were added.	For clarity

SAP Amendment	Section	Major Revision	Rationale
#1	Section 10.1	
1. The primary analysis was updated to use stratified log-rank test instead of unstratified log-rank test
 
2. The first sensitivity analyses was updated.
	
1. To ensure each analysis stratum has sufficient number of events, the log-rank test is stratified by modified index episode (manic and depressed) only. Manic index episode (s) with or without mixed features will be classified as manic episode(s); depressive index episode(s) with or without mixed features will be classified as depressive episode(s).
 
2. Previous proposed first sensitivity analyses was deleted because of the duplication (time to all-cause discontinuation is one of other efficacy analyses in Section 7.3.3). Newly added delta-adjusted method by Zhao et al. (2014) aligned with the discussion with FDA for schizophrenia maintenance sNDA filing (based on single study RGH-MD-06).

#1	Section 11.1	All text to define how AEs and TEAEs will be coded and summarized was replaced.	To reflect current sponsor standards
#1	Section 11.1	All text about NEAE was deleted.	To reflect current sponsor standards
#1	Section 11.1	All text about TESAE definition and related analysis was added.	To reflect current sponsor standards
#1	Section 11.1	The period for reporting of pregnancies during the study from 30 days after last dose was changed to approximately 12 weeks following last dose.	These are standard components of a slit-lamp examination.
#1	Section 11.1	[REDACTED]	[REDACTED] updated before data base lock.
#1	Section m11.2	The text for analysis of central lab transition during the clinical trial was added.	The central lab was changed from Q2 to Covance during the clinical trial.
#1	Section 11.2	The analysis for some urinalysis parameters was deleted.	These urinalyses deleted were not measured.

SAP Amendment	Section	Major Revision	Rationale
#1	Section 11.2	The analysis on some lab parameters in conventional units was added.	To reflect current sponsor standards
#1	Section 14.0	Sample size was changed.	Sample size was modified for the following reasons 1. As the study population changed due to inclusion criteria changes, related assumptions were modified. The assumed probability of relapse in the placebo arm at Week 39 was updated to 50%. 2. The assumed hazard ratio was updated to reflect modified relapse data based on feedbacks from FDA review of maintenance filing for study RGH-MD-06.
#1	Table 16.1-1, Table 16.1-2, Table 16.1-3	Analysis windows were changed.	To align with updated visit schedule.
#1	Section 17.0	Paragraphs to describe the changes to analyses specified in protocol were added.	To align with Protocol Amendment #3.
#2	Table 4-2	Updated table.	To align with COVID-19 Global Protocol Addendum and Protocol Amendment #5
#2	Section 7.1	Added summary of number and percentage of patients in each analysis population.	For completeness
#2	Section 8.0	Defined baseline efficacy variables for OLTP and DBTP	For clarity
#2	Section 10.1	Added subgroup analyses for primary efficacy parameter by age group, sex, race, region and modified index episode.	Evaluate the efficacy in different subgroups
#2	Section 10.3	Listed additional efficacy parameters for OLTP and DBTP	For clarity
#2	Section 11.1	Added summary of TEAEs during the OL SFU period and DB SFU period	Evaluate safety in safety follow-up periods
#2	Section 11.2	Added summary for potential Hy's Law cases during the OLTP and DBTP.	Evaluate liver function tests
#2	Section 11.2	Added Table 11.2-2	Define criteria for treatment-emergent significant changes in glucose

SAP Amendment	Section	Major Revision	Rationale
#2	Section 11.2	Added Table 11.2-3	Define criteria for treatment-emergent significant changes in lipids
#2	Section 14.0	Revised assumptions for sample size determination	To align with protocol Amendment #5
#2	Section 16.1	Added Table 16.1-2	Define analysis windows in OLTP for lab and waist circumference parameters
#2	Section 16.1	Added Table 16.1-3	Define analysis windows in OLTP for PSP
#2	Section 16.1	Added Table 16.1-4	Define analysis windows in OLTP for EPS
#2	Section 16.1	Added Table 16.1-6	Define analysis windows in DBTP for lab and waist circumference parameters
#2	Section 16.1	Added Table 16.1-7	Define analysis windows in DBTP for PSP
#2	Section 16.1	Added Table 16.1-8	Define analysis windows in DBTP for WPAI-BD
#2	Section 16.1	Added Table 16.1-9	Define analysis windows in DBTP for EPS
#2	Section 17.0	New section specifying analyses for evaluating the impact of COVID-19	Evaluate impact of COVID-19
#3	Section 6.7	Updated the DB ITT population definition by including patients with relapse event but no efficacy assessments.	To account for relapses during the double-blind treatment period for patients without any efficacy assessments.
#3	Sections 10.1 and 10.3 and SAS codes in Appendices	Added 'region' to the models.	The study was stratified by region as well.
#3	Section 10.1	Updated age cutoff from 55 to 45 years.	Due to imbalance of age categories for 55 cutoff based on blinded data review.
#3	Section 10.1	New sensitivity analysis of primary endpoint, censoring ongoing Russian and Ukrainian participants after 24Feb2022.	Due to Russian-Ukrainian conflict that began on 24Feb2022.
#3	Section 10.1	Added 2 Kaplan-Meier figures.	To explore data further.
#3	Section 12.0	Updated text in WPAI.	WPAI description was missing.

SAP Amendment	Section	Major Revision	Rationale
#3	Section 12.0	Removed “The medical resource utilization and health economics assessments will be specified in a separate prospective analysis plan. “	No longer the process. HEOR now is part of this SAP document.
#3	Section 16.3	[REDACTED]	[REDACTED]
